10.4.3 Evaluation of Best Response

The best overall response is the best response recorded from the start of the treatment until disease progression/recurrence (taking as reference for progressive disease the smallest measurements recorded since the treatment started). The patient's best response assignment will depend on the achievement of both measurement and confirmation criteria.

10.4.4 Overall Response Rate

Overall Response Rate (OR) = CR + PR based on evaluation of best response in each patient.

11. Data Reporting / Regulatory Requirements

Adverse event lists, guidelines, and instructions for AE reporting can be found in Section 7 (Adverse Events: List and Reporting Requirements).

11.1 Data Reporting

11.1.1 Monitoring

The Institutional Review Board (IRB) at each respective institution will monitor this study.

11.1.2 Responsibility for Data Submission

The Study Coordinator is responsible for compiling data for all participants and for providing the data to the Study Chair for review.

11.2 Data Safety Monitoring Board

The Herbert Irving Comprehensive Cancer Center at Columbia University Medical Center's Data Safety Monitoring Board (DSMB) will oversee conduct of the study, patient safety and all interim analyses as specified in the data analysis plan. Detailed guidelines regarding the structure, function and decision-making mechanisms for the Data Safety Monitoring Board are provided in the DSMB charter.

11.3 Investigator Reporting Responsibilities and Compliance

The conduct of the study will comply with all FDA safety reporting requirements.

During the course of the study, the Sponsor may determine that certain safety reports are required to comply with regulations. The Sponsor is responsible for submission of such reports to their IND. The Investigator may receive a letter called an “IND Safety Report” from this study and/or other Acetylon sponsored studies (cross reports). These reports are required to be submitted to the IRB/EC.

11.4 Study auditing

Investigator responsibilities are set out in the ICH guideline for Good Clinical Practice (GCP) and in the US Code of Federal Regulations.

Investigators must enter study data onto CRFs or other data collection system. The Investigator will permit study-related audits by CUMC, Acetylon or its representatives, IRB/EC review, and regulatory inspection(s) (e.g., FDA, EMEA, TPP), providing direct access to the facilities where the study took place, to source documents, to CRFs, and to all other study documents.

11.5 Protocol amendments

Any amendment to this protocol must be agreed to by the Principal Investigator and reviewed by CUMC and Acetylon. Amendments should only be submitted to IRB/EC after consideration from CUMC and Acetylon review. Written verification of IRB/EC approval will be obtained before any amendment is implemented.

12. Statistical Considerations

12.1 Statistical Methods

12.1.1 Phase Ib:

The study will follow the similar principles of a standard 3+3 dose escalation study in which less than one third of patients enrolled to a particular Arm must not have a dose limiting toxicity to allow for expansion. Three patients will be sequentially enrolled in one of two cohorts: Arm A and then after a safety assessment has occurred, Arm B for a total of six patients (3 in each arm). If $\leq 33\%$ of patients ($N \leq 1$) experiences a dose limiting toxicity (DLT) in a cohort, the cohort will be expanded to 6 patients. If there are $\leq 33\%$ ($N \leq 2$ DLTs), the cohort will be further expanded to a total of 10 patients (3+3+4). The total number of patients for both Arms A and B with full expansions will total of 20. If more than 1/3 or 2/6 patients experience a DLT, there will be no expansion. Safety data obtained from this Phase Ib will be analyzed by the sponsor and collaborating investigators to recommend a Phase II dose.

12.1.2 Phase II:

The study will employ the minimax Simon 2-stage design. In Stage 1, 22 patients will be enrolled. If < 2 patients experience an objective tumor response (defined as CR, or PR, as outlined by the 2007 International Harmonization Project criteria), the study will be discontinued. If 2 or more of the first 22 patients experiences CR, or PR, additional 18 patients will be enrolled in Stage 2. Enrollment into Stage 2 will begin only after least 2 objective response have been observed in Stage 1. (Enrollment into Stage 2 need not be delayed until the response status of all 22 Stage 1 patients is known.) The design parameters are as follows:

- 0.15: unacceptable response rate.

- 0.25: target response rate.
- $\alpha = 0.05$: the probability of declaring the drug effective when the true response probability is less or equal to 0.15.
- $\beta = 0.20$: the probability of declaring the drug as not effective when its true response probability is as large or larger than the target response rate 0.30.

Once enrollment begins for stage 2 of the study, an additional 20 patients will be enrolled per lymphoma subtype, specifically Mantle Cell Lymphoma. Therefore the total number of patients estimated to be enrolled is 60.

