This is a phase II, single-arm, multicenter, open-label study in patients with relapsed or relapsed/refractory lymphoma. Utilizing the Simon 2 Stage Minimax design, an estimated 40 patients will be needed to determine efficacy at a power of 0.80 and type I error of 0.05. Using this design, there will be an early stopping rule if $< 10\%$ achieve a response in Stage 1. Twenty-two ($N=22$) patients will be accrued to Stage 1, of which 2 patients are required to achieve a response to allow accrual to Stage 2. Patients accrued to Stage 1 of the Phase II will be of all lymphoid malignancy subtypes including those with mantle cell lymphoma (MCL). Eighteen patients ($N=18$) will be treated in Stage 2, of which 8 responses would be needed to attain an efficacy of at about 25%. The safety, tolerability, single- and multiple-dose PK, pharmacodynamics, and anti-tumor activity of ACY-1215 also will be evaluated. Simultaneously in Stage 2, an additional cohort of 20 mantle cell lymphoma patients will be assessed to evaluate for a signal of efficacy in this subtype. These patients will be enrolled in parallel to the phase II study. Assuming success in Stage I, enrollment to Stage 2, and expansion of MCL cohort, the total number of patients will be 60 (Stage 1 $N=22$, Stage 2 $N=18$, MCL focused Expansion Phase $N=20$).

5.1.3 Treatment plan common to both Phase Ib and Phase II:

After executing written informed consent, patients will be evaluated for study eligibility during the Screening period within the Screening period before Cycle 1, Day 1 [C1D1]. Patients determined to be eligible will be treated on study. Patients will be evaluated on Days 1, 8, and 15 of Cycle 1.

On study drug administration days that coincide with scheduled study center visits, ACY-1215 will be administered at the study center.

- One cycle of therapy is comprised of 28 or 56 doses of ACY-1215.
- Administration of the study drugs will be allowed within 48 hours of the scheduled dates.
- Missed doses will not be made up.

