12.9.1.2 Phase II

Interim analysis will be performed following accrual of the first 22 patients to ensure a response rate of at least 10% to proceed to stage 2 of accrual. An early stopping rule will be in effect if <10% of patients achieve a response. If >10% achieve a response, Stage 2 will proceed.

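### The Stage 1 go rule of 2 responses in 22 does not fit the stated Simon minimax design: it passes 86% of trials at the protocol's 15% unacceptable rate and is one response too lenient even for a 10% null

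*Combined protocol and SAP*

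**What the plan says.** The Phase II count rule appears in three places. Section 12.1.2 states "If 2 or more of the first 22 patients experiences CR, or PR, additional 18 patients will be enrolled in Stage 2". Section 5.1.2 (Phase II) describes 22 Stage 1 patients, "of which 2 patients are required to achieve a response to allow accrual to Stage 2". The synopsis also asks for 2 responses among 22.

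A percentage rule sits beside it. Section 12.9.1.2 describes the interim analysis as intended "to ensure a response rate of at least 10% to proceed to stage 2 of accrual", with stopping below 10% and continuation above it. Section 5.1.2 also mentions stopping below 10%.

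The design parameters in 12.1.2 are "0.15: unacceptable response rate" and "0.25: target response rate". Alpha of 0.05 is defined as "the probability of declaring the drug effective when the true response probability is less or equal to 0.15". The beta entry refers instead to a true rate "as large or larger than the target response rate 0.30". The total is 40 patients (22 + 18) with power 0.80, and 8 responses are needed at the end.

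The MCL cohort is tied to the same gate: "Once enrollment begins for stage 2 of the study, an additional 20 patients will be enrolled per lymphoma subtype, specifically Mantle Cell Lymphoma".

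**The concern.** A futility gate in a Simon design should stop a drug at the unacceptable rate reasonably often. Here both stated cut-offs (9.1% as a count, 10% as a percentage) lie below the 15% that the protocol calls unacceptable. At 15%, Stage 1 is expected to give 22 × 0.15 = 3.3 responses, so a result below the null expectation counts as a pass. The two cut-offs also disagree when exactly 2 patients respond.

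What is at stake is the exposure of up to 18 + 20 = 38 further patients with relapsed or refractory lymphoma after Stage 1, and whether the interim look does the job expected of a minimax design. The gate depends only on Stage 1 responses, so correcting the final cut-off alone would leave it as it is.

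**Working it through.** **Inputs.** From 12.1.2: n1 = 22, n2 = 18, go at 2 or more, p0 = 0.15, p1 = 0.25 (0.30 in the beta entry), alpha 0.05, power 0.80. From 12.9.1.2: a 10% threshold; 10% of 22 is 2.2, so in practice 3 or more. From the synopsis and 5.1.2: 8 responses at the end. I read this as 8 or more of all 40, because 8 of the 18 Stage 2 patients alone would be 44%, not about 25%.

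**Step 1. Can the plan's own figures be reproduced?** I searched exhaustively for the Simon minimax design with alpha ≤ 0.05 and power ≥ 0.80.

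| p0 v p1 | Stop Stage 1 at | Reject drug at | Alpha | Power | P(early stop at p0) |
|---|---|---|---|---|---|
| 0.15 v 0.25 | ≤8 of 55 | ≤20 of 97 | 0.049 | 0.801 | 0.56 |
| 0.15 v 0.30 | ≤3 of 23 | ≤11 of 48 | 0.045 | 0.804 | 0.54 |
| 0.10 v 0.25 | ≤2 of 22 | ≤7 of 40 | 0.040 | 0.803 | 0.62 |

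Forty patients do not follow from a 0.15 null with either target. The sizes 22 and 40 and the final count of 8 are exactly the 0.10 v 0.25 design. In that design 2 of 22 is the stopping boundary and continuation needs 3.

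**Step 2. Probability of passing Stage 1.** P(go) is the upper binomial tail with n = 22.

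For p = 0.15:
- P(0) = 0.85^22 = 0.0280
- P(1) = 22 × 0.15 × 0.85^21 = 0.1087
- P(2) = 231 × 0.15² × 0.85^20 = 0.2015
- P(≥2) = 1 − 0.0280 − 0.1087 = 0.863
- P(≥3) = 0.863 − 0.2015 = 0.662

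| True rate | Go at ≥2 | Go at ≥3 |
|---|---|---|
| 5% | 30.2% | 9.5% |
| 10% | 66.1% | 38.0% |
| 15% | 86.3% | 66.2% |
| 25% | 98.5% | 93.9% |

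**Step 3. Expected Phase II enrolment**, counting Stage 2 and the MCL cohort: 22 + 38 × P(go).
- At 15%: 22 + 38 × 0.8633 = 54.8 with the count rule; 22 + 38 × 0.6618 = 47.1 with 3 or more.
- At 10%: 47.1 and 36.4.

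**Step 4. Whole-trial properties.** P(success) = Σ P(X1 = x) × P(X2 ≥ r − x), summed over Stage 1 counts x at or above the gate, where r is the final cut-off.

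| Gate | Final cut-off | Alpha at 10% | Alpha at 15% | Power at 25% | Power at 30% |
|---|---|---|---|---|---|
| ≥2 | ≥8 of 40 | 0.042 | 0.243 | 0.816 | 0.944 |
| ≥3 | ≥8 of 40 | 0.040 | 0.234 | 0.803 | 0.936 |
| ≥4 | ≥8 of 40 | 0.034 | 0.206 | 0.754 | 0.904 |
| ≥2 | ≥11 of 40 | 0.002 | 0.030 | 0.416 | 0.691 |
| ≥4 | ≥11 of 40 | 0.001 | 0.029 | 0.409 | 0.684 |

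With a 0.15 null and 40 patients, 11 of 40 is the smallest final cut-off that holds alpha at 0.05 (10 of 40 gives 0.064 to 0.067 for gates of 2 to 4).

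**The case against.** The strongest objection is that the gate is a symptom and not a separate defect. The 86% rests on p0 = 0.15, the input that the rest of the design contradicts. If the null is really 0.10, the percentage rule already in 12.9.1.2 (3 or more of 22) is the correct gate. This largely stands, and it is why the null has to be settled together with the count. It does not rescue the count rule, which is stated in three places and is too lenient under either null.

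A reader might infer that the gate hardly ever operates or carries almost no information. The figures do not support that in general. Fifteen per cent is the upper edge of the unacceptable range; at a true 5% the count rule stops about 70% of trials and the percentage rule about 91%. At 3 or more, the contrast of 66.2% with 93.9% is real discrimination. Nor is 2 of 22 clearly worse than unacceptable: its exact 95% interval, 1.1% to 29.2%, includes both 15% and 25%.

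A reader might also infer that a gate of 4 of 22 is the natural remedy for a 15% null. With the protocol's 8 of 40 it would lower power at 25% to 0.754, below the stated 0.80, and leave alpha at 0.206.

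Two further points are fair. The gate is the only futility stop, but patients have other protection: 5.1.2.2 requires a safety review before Stage 2 and the MCL cohort, and 11.2 places interim analyses under a monitoring board. The MCL cohort also has its own signal-seeking aim, and a stricter gate based on patients of all subtypes could block it on mainly non-MCL data. Moving from 2 to 3 responses limits that cost but does not remove it.

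**Conclusion.** The concern holds for the decision threshold. The written count rule is inconsistent with the stated 15% unacceptable rate (86.3% of trials pass at exactly 15%), and it is one response more lenient than the minimax design whose sizes and final count the protocol uses (66.1% pass at 10%, where that design passes 38.0%). The percentage rule matches that design at a 10% null, but still passes 66.2% of trials at 15%.

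This rests on reading the final criterion as 8 of 40 in total and on exact binomial calculation with a common response rate. It also assumes that all 22 patients count in the Stage 1 decision. That 0.10 was the intended null, and that a stopping boundary was written down as a go threshold, is an inference from the recomputation; the documents do not say so. The gate is one part of a wider mismatch among p0, p1 and the two boundaries, and changing it alone is not sufficient if 0.15 is kept.

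**What to change.** Use one Stage 1 rule in the synopsis, 5.1.2 (Phase II), 12.1.2 and 12.9.1.2: *stop if 2 or fewer of the first 22 patients respond; open Stage 2 and the MCL cohort at 3 or more.* Delete the 10% wording. In 12.1.2, also change the sentence that lets Stage 2 begin once 2 responses have been seen, so that it requires 3. If the sponsor confirms the 0.10 v 0.25 design, restate the unacceptable rate as 0.10 and the target as 0.25 throughout, including the alpha and beta entries. State the final criterion as 8 or more of 40. Give the achieved alpha (0.040), power (0.803) and early-termination probability under the null (62%).

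The cost is an amendment and no extra patients. Power at 25% falls by 1.3 points (0.816 to 0.803), and false stopping at a true 25% rises from 1.5% to 6.1%. Of those newly stopped trials, (0.8161 − 0.8032) / (0.9851 − 0.9394) = 28% would have met 8 of 40.

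If the sponsor keeps 0.15 as the null, both boundaries and the sample size must be re-derived together and the achieved alpha, power and early-stopping probability stated. Within 40 patients, 8 of 40 leaves alpha at 0.21 to 0.24 for gates of 2 to 4, and 11 of 40 leaves power at about 0.41 at 25% and 0.69 at 30%. The minimax designs that meet the stated error rates need 48 patients (target 0.30) or 97 (target 0.25). A stand-alone gate of 4 of 22 should not be prescribed.

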- The anti-tumor activity of ACY-1215, as measured by:
 - Objective response rate (complete response [CR] + partial response [PR]) assessed according to International Harmonization Project revised Criteria (2007)

Secondary endpoints of the study are to:

- Define the duration of response
- Define the rate of progression free survival
- Define safety and adverse events
- Define the exposure response analyses including biomarkers relating to intracellular protein acetylation.
- Describe the Single- and multiple-dose ACY-1215 pharmacokinetic profile.
- Describe changes in MRS signals with response to study drug

Sample Size

Phase Ib:

Three patients will be sequentially enrolled in one of two cohorts: Arm A and Arm B for a total of six patients (3 in each arm). If $\leq 33\%$ of patients ($N \leq 1$) experiences a dose limiting toxicity (DLT) in a cohort, the cohort will be expanded to 6 patients (3+3). If there are $\leq 33\%$ ($N \leq 2$ DLTs), the cohort will be further expanded to a total of 10 patients (3+3+4). The maximum total number of patients for both Arms A and B with full expansions will total of 20. If more than 1/3 or 2/6 patients experience a DLT, there will be no expansion.

Phase II:

Utilizing the Simon 2 Stage Minimax design, an estimated 40 patients will be needed to determine efficacy at a power of 0.80 and type I error of 0.05. For Stage I, 22 patients

will be enrolled of which 2 must achieve a response to allow for recruitment of patients into Stage 2. Stage 2 will enroll 18 patients of which 8 responses would be needed to attain an efficacy of 25%. An expansion cohort of 20 patients with relapsed or refractory mantle cell lymphoma patients will be assessed to evaluate efficacy in this subtype. The total number of patients accrued to the Phase II component of the study will equal 60.

Safety

Patients will be monitored carefully for the development of adverse events as well as clinical and/or radiographic evidence of disease response. Adverse events will be evaluated according to criteria outlined in the NCI Common Terminology Criteria for Adverse Events (CTCAE), version 4.0.

Figure 1: Schema

[figure not shown]

TABLE OF CONTENTS

	Page
1. OBJECTIVES	1
1.1 Phase Ib	1
1.2 Phase II	1
2. BACKGROUND	1
2.1 Background on lymphoid Malignancies	1
2.2 ACY-1215	2
2.3 Rationale for Phase Ib Study Design	11
3. PATIENT SELECTION	12
3.1 Inclusion Criteria for Lymphoma	12
3.2 Exclusion Criteria	13
3.3 Inclusion of Women and Minorities	13

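### The Phase II design parameters (null 0.15, target 0.25 or 0.30, 5% alpha, 80% power) cannot be met by 22 + 18 = 40 patients, and the final success threshold can be read three ways

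*Combined protocol and SAP*

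**What the plan says.** Section 12.1.2 (Phase II) specifies a minimax Simon two-stage design with these parameters:

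- null: "0.15: unacceptable response rate"
- target: "0.25: target response rate"
- alpha 0.05, defined as "the probability of declaring the drug effective when the true response probability is less or equal to 0.15"
- beta 0.20, defined where "its true response probability is as large or larger than the target response rate 0.30"

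The Stage 1 rule there is a count: "If 2 or more of the first 22 patients experiences CR, or PR, additional 18 patients will be enrolled in Stage 2". The section gives no final success threshold.

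The only final threshold is in the synopsis (Sample Size) and Section 5.1.2 (Phase II). The synopsis says: "Stage 2 will enroll 18 patients of which 8 responses would be needed to attain an efficacy of 25" per cent. Section 5.1.2 says: "will be treated in Stage 2, of which 8 responses would be needed to attain an efficacy of at about 25" per cent. Both claim power 0.80 and type I error 0.05 with 40 patients, and both let the trial continue on 2 responses in Stage 1.

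Sections 5.1.2 and 12.9.1.2 also give the interim rule as a percentage: stop below 10%. Section 12.9.1.2 adds that Stage 2 proceeds above 10%.

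**The concern.** Two rates are called the target within a few lines, and it is not clear that either is compatible with 40 patients when the null is 0.15. The final threshold does not fit its own percentage either: 8/18 is 44%, 8/40 is 20%, and only 10/40 is 25%.

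Response rate is the Phase II primary endpoint in the synopsis, and the Simon rule is its only decision rule. If the parameters and threshold do not fit together, a claim of activity has no known false-positive rate. The reading chosen can also decide the result. The trial is open-label, so a threshold settled once responses are known would be data-driven.

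**Working it through.** **Inputs.** From Section 12.1.2: n1 = 22, n2 = 18, continue at ≥2/22, p0 = 0.15, p1 = 0.25 or 0.30, alpha 0.05, beta 0.20. From the synopsis and Section 5.1.2: 8 responses, 25%, N = 40.

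**Formula.** Let X ~ Bin(22, p) and Y ~ Bin(18, p). With Stage 1 cut-off a and cumulative threshold c,

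P(success | p) = Σ (x = a to 22) P(X = x) · P(Y ≥ c − x).

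For the literal 8-of-18 reading it is P(X ≥ 2) · P(Y ≥ 8).

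**Step 1: reproduce N = 40.** An exact minimax search (alpha ≤ 0.05, power ≥ 0.80) gives:

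| p0 | p1 | Stop at | Not active at | Alpha | Power |
|---|---|---|---|---|---|
| 0.15 | 0.25 | ≤8/55 | ≤20/97 | 0.0488 | 0.8011 |
| 0.15 | 0.30 | ≤3/23 | ≤11/48 | 0.0455 | 0.8035 |
| 0.10 | 0.25 | ≤2/22 | ≤7/40 | 0.0398 | 0.8032 |

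The stated parameters give 97 or 48, not 40. The sizes 22 and 40 reproduce with p0 = 0.10 and p1 = 0.25, but that design stops at 2/22, where the protocol's count rule continues.

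**Step 2: can any cut-offs rescue 22 + 18?** I searched every Stage 1 cut-off and final threshold with alpha ≤ 0.05 at 0.15. The best rule is success at ≥11/40 (alpha 0.030), with power 0.416 at 0.25 and 0.691 at 0.30. Allowing every two-stage split of 40 raises these only to 0.487 and 0.745.

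**Step 3: the three readings, continuing at ≥2/22.**

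| Reading | Type I error at 0.15 | Power at 0.25 | Power at 0.30 |
|---|---|---|---|
| ≥8 of the 18 in Stage 2 (literal) | 0.002 | 0.056 | 0.140 |
| 2 + 8 = 10, i.e. ≥10 of 40 (25%) | 0.067 | 0.560 | 0.804 |
| ≥8 of 40 (20%) | 0.243 | 0.816 | 0.944 |
| Stated | 0.05 | 0.80 | 0.80 |

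For the literal reading at 0.15: P(X ≥ 2) = 0.8633 and P(Y ≥ 8) = 0.0027, product 0.0023. No reading meets both stated error rates at either target.

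**Step 4: how often the reading decides the result.** With ≥2 responses in Stage 1, a total of 8 or 9 of 40 succeeds only under the 8-of-40 reading; at most 7 of those responses can fall in Stage 2, so 8 of 18 fails too. Its probability is 0.2427 − 0.0672 = 0.176 at a true rate of 0.15, and 0.8161 − 0.5602 = 0.256 at 0.25.

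**Step 5: the interim rules.** 2/22 = 9.1%, below 10%; 3/22 = 13.6%. The count rule continues at 2 and the percentage rule stops. Exactly 2/22 has probability 0.281 at a true rate of 0.10 and 0.201 at 0.15. Early stopping is:

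| Continue at | True rate 0.10 | True rate 0.15 |
|---|---|---|
| ≥2/22 | 0.339 | 0.137 |
| ≥3/22 | 0.620 | 0.338 |

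**The case against.** The strongest reply is that the sample size is sound and the parameter bullets are mistyped. With p0 = 0.10, p1 = 0.25, continuation at ≥2/22 and success at ≥8/40, alpha is 0.0416 and power 0.8161, so both stated error rates are met. This may well be what was meant. But 0.15 appears in both the null and the alpha bullets, 10% appears only as the Stage 1 percentage, and no section gives 0.10 as the unacceptable rate. It remains an inference that the sponsor must confirm.

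Second, 8 of 18 is a weak reading because 44% contradicts the 25% in the same sentence. That is fair. Setting it aside still leaves type I error at 0.067 or 0.243.

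Third, Section 12.3.2.1 plans an estimated response rate with an exact 95% confidence interval, which stays interpretable, and Section 12.11 promises a formal statistical plan before database lock. The interval supplies no decision rule, and the promised plan is a place for the correction rather than the correction itself.

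Fourth, the interim conflict barely moves the final error rates: at 0.15, going from ≥2/22 to ≥3/22 changes alpha from 0.0672 to 0.0666 (10/40) or from 0.2427 to 0.2343 (8/40). That stands. Its effect is on whether the trial stops early.

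**Conclusion.** The concern holds. As written, the null, alpha, power and sample size cannot all be true under either target, and the success threshold is not uniquely defined. Power at 22 + 18 is at most 0.416 or 0.691 against the stated 0.80. Type I error at 0.15 runs from 0.002 to 0.243 across the readings, or from 0.067 to 0.243 without the literal one. The interim rule gives opposite answers at 2/22.

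The figures are exact binomial probabilities. They assume 22 and 40 response-evaluable patients. Sections 4.5 and 6.1 replace patients who miss more than 10% of planned dose, and Section 12.3.2.1 treats those who leave before response evaluation as un-evaluable, so the attained rates hold only if those denominators are kept.

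**What to change.** Before any analysis of Stage 2 results, the sponsor should confirm one p0, one p1 (the same in the target and beta bullets), one Stage 1 cut-off among the first 22 patients and one cumulative success threshold among the 40. State these with the attained error rates identically in the synopsis and Sections 5.1.2, 12.1.2 and 12.9.1.2. The options at n = 40, each conditional on that confirmation, are:

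- **(a) p0 = 0.10 and p1 = 0.25 are confirmed.** Success at ≥8/40. Continuing at ≥2/22 gives alpha 0.042 and power 0.816, and the 10% wording must be corrected. Continuing at ≥3/22 gives alpha 0.040 and power 0.803; it changes the stated count and raises early stopping from 0.34 to 0.62 at a true rate of 0.10, and from 0.14 to 0.34 at 0.15.
- **(b) p0 = 0.15 is kept, continuing at ≥2/22.** Drop the joint 5%/80% claim, correct the 10% wording so that 2/22 continues, and report the attained figures for the threshold that was meant:

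| Threshold | Alpha at 0.15 | Power at 0.25 | Power at 0.30 |
|---|---|---|---|
| ≥8/40 | 0.243 | 0.82 | 0.94 |
| ≥10/40 | 0.067 | 0.56 | 0.80 |
| ≥11/40 | 0.030 | 0.42 | 0.69 |

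Keeping p0 = 0.15 together with 5% and 80% would mean re-sizing to 48 or 97, which is 8 or 57 more patients, and is not needed to make the plan coherent.

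**Cost.** No extra patients at n = 40. Restating the parameters is a wording change in four places, submitted under the approval steps in Sections 11.5 and 14.5. Setting success at 8/40 if 10/40 was meant, or moving continuation to ≥3/22, changes a decision rule and needs an amendment in substance. The price is a weaker null claim (10% instead of 15%) or less favourable stated error rates.
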